## **Objectives**

1. To determine the correlation between vitamin D status and quadriceps muscle strength at pre-op and at 4 months after ACLR.
2. To conduct a randomized-controlled trial to examine the therapeutic effects of vitamin D supplement on improving vitamin D deficiency status in patients with quadriceps muscle weakness after ACLR.
3. To examine the effect of vitamin D supplements on the quadriceps muscle strength for patients after ACLR.

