## Patient Recruitment & Eligibility

This is a prospective randomized, double-blinded placebo-controlled trial with all participants being recruited at the out-patient clinic of Prince of Wales Hospital. Participants are randomly assigned into either the Vitamin D intervention group or the placebo-controlled group through an online computer generator sequence at the time of admission to the out-patient clinic. 60 participants will be recruited, with 30 in each group. The study will be carried out in compliance with Declaration of Helsinki and the ICH-GCP. Ethical approval will be obtained from the local IRB before the study starts. Informed consent must be obtained from all patients in order to participate in the study.

Participants will be recruited according to the following criteria:

Inclusion Criteria	Exclusion Criteria

1) Aged 18-40 with unilateral ACL injury

2) Sporting injury with a Tegner score of 7

3) Pre-op serum vitamin D level <math><20\text{ng/ml}</math>

4) 4 months post-ACLR with serum Vitamin D level remained <math><20\text{ng/ml}</math>

5) LSI for quadriceps strength <math><70\%</math> of contralateral leg at 4-month isokinetic assessment

6) Both knees without history of injury/prior surgery

	

1) Concomitant bone fracture, major meniscus injury or full-thickness chondral injuries requiring altered rehabilitation program post-operatively

2) Pre-operative radiographic signs of arthritis

3) Metal implants that would cause interference on MRI

4) Non-HS graft for ACLR

5) Patient non-compliant to the rehabilitation program

6) Regular sunbed users

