### Outcome Measurements

#### 1. Anthropometric Measurement

Body Mass Index (BMI) would be calculated by the measured height and weight at 4 months post ACLR before vitamin D supplements, during the eighth week of vitamin D supplements, after the completion of 16 weeks vitamin D supplements, and 12-months post-operation. We would measure the waist circumference as well. Subcutaneous fat would be measured using skinfold techniques for the triceps brachii and biceps brachii.

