## **Sample Size Estimation and Power Calculation**

For objective 1, when the sample size is 92, a bivariate correlation test will have 90% power to detect at the 0.050 level with a correlation coefficient of 0.3. The proposed sample size (150) will be sufficient to detect the difference and enables the fulfillment of objective 2 and 3 in this study (with an estimated 40% quadriceps strength deficit at 4-month post-op). For objective 2, when the sample size in each group is 30, a repeated-measure ANOVA (with three repeated measures) will have 90% power to detect at the 0.050 level, with an effect size of 0.35. (G\*Power 3.1.9.4).

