## **Data Processing and Analysis**

Data will be reported as the mean  $\pm$  standard error of the mean, except for non-normally distributed data which are reported as the median, minimum and maximum. All Statistical analysis will be performed using the Statistical Package for Social Sciences (SPSS) 25. Statistical significance will be set at  $p < 0.05$ . For objective 1, a bivariate Pearson's correlation will be used to detect correlation between serum vitamin D levels and muscle strength and size at 4-month post-op, controlled for anthropometric variables. For objective 2, data will be analyzed by a repeated-measure ANCOVA (Control vs vitD supplementation; with repeated measures at 4-, 8-, 12-month post-op; other anthropometric variables as covariance). Primary outcome would be quadriceps muscle strength. These statistical tests will be performed after checking the normal distribution with Kolmogorov-Smirnov test, otherwise, a non-parametric

equivalent will be used. The “Intention-to-Treat” principle will be followed for data analysis purposes on those who have completed 16-week treatment. “Protocol Evaluable Analysis” will also be conducted using the 80% compliance as the cut-off. This trial will be registered at a clinical trial registry ([ClinicalTrials.gov](https://www.clinicaltrials.gov)) before the study is implemented.

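### The pre-treatment 4-month strength value is modelled as a repeated outcome instead of a baseline covariate: valid, but it gives up power, most of all if the test is a three-visit group main effect

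*Protocol*

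**What the plan says.** The Data Processing and Analysis section specifies a "repeated-measure ANCOVA (Control vs vitD supplementation; with repeated measures at 4-, 8-, 12-month post-op" and, as covariates, "other anthropometric variables as covariance". It adds "Primary outcome would be quadriceps muscle strength". It does not say whether the treatment is judged by the group main effect, the group-by-time interaction or a contrast at one visit.

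The 4-month visit comes before treatment. The Anthropometric Measurement section describes it as "4 months post ACLR before vitamin D supplements", and the Radiological Assessment section places it before supplementation too. Strength is already measured then, because eligibility depends on the limb symmetry index relative to that "of contralateral leg at 4-month isokinetic assessment".

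The Sample Size section begins "For objective 2, when the sample size in each group is 30" and continues "a repeated-measure ANOVA (with three repeated measures) will have 90% power to detect at the 0.050 level, with an effect size of 0.35". Objective 2 concerns vitamin D status. Strength is objective 3: "To examine the effect of vitamin D supplements on the quadriceps muscle strength for patients after ACLR".

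**The concern.** A value taken before treatment cannot carry a treatment effect, yet it is one of the three outcome levels. Two consequences follow.

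- If the conclusion rests on the group main effect, the estimate averages in a visit whose expected difference is zero. A difference of 0.70 SD at both later visits becomes 2 × 0.70 / 3 = 0.47 SD.
- If it rests on the group-by-time interaction, the test is sound. It does not, however, make the best use of the 4-month value, which would normally enter as a covariate.

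The power statement does not settle which is meant: it names neither the term nor the correlation between visits. It is also labelled for objective 2, while the Data Processing section makes strength the primary outcome of the same model. With 60 participants, the risk is missing a real effect.

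**Working it through.** **Inputs from the protocol:** 30 per group (N = 60), three measures, alpha 0.05, f = 0.35, stated power 90%. **Assumed:** SD 1 at each visit, equal correlation ρ between visits (0.3 / 0.5 / 0.7 / 0.8), no losses. Read as a two-group effect size, f = 0.35 is 2 × 0.35 = 0.70 SD.

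**1. Reproducing the 90%**

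- *Group main effect over three visits:* λ = f²·N·3/(1+2ρ), F(1,58). At ρ = 0.5, λ = 0.1225 × 180 / 2 = 11.03 and power is 90.4%; N = 58 gives 89.4%. At ρ = 0.3 / 0.7 / 0.8 it is 95.5 / 84.6 / 81.7%.
- *Interaction, G\*Power 'as in SPSS' option:* λ = 0.1225 × 58 × 2 = 14.21, F(2,116), power 92.5% with no ρ needed. Here f = 0.35 is not 0.70 SD; it equals a sustained difference of 1.00 / 0.84 / 0.65 / 0.53 SD at the four correlations.
- *Interaction, default option:* power above 99.9%; at ρ = 0.5, N = 20 would suffice.

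The main effect at ρ = 0.5 is the closest match, but the 'as in SPSS' interaction also satisfies the statement.

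**2. Power when the effect can arise only after treatment starts**

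Let d be the vector of group differences at 4, 8 and 12 months, with d4 = 0.

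- Main effect: λ = mean(d)² / [((1+2ρ)/3)(2/30)], F(1,58).
- Interaction: λ = 15·Σ(d − mean d)²/(1−ρ), F(2,116).
- Joint baseline-adjusted test: λ = 15·v′S⁻¹v with v = (d8, d12) and S = [[1−ρ², ρ−ρ²],[ρ−ρ², 1−ρ²]], F(2,56).

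For a sustained 0.70 SD at ρ = 0.5:

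- Main effect: λ = 0.4667² / (0.6667 × 0.0667) = 4.9, power 58.6%.
- Interaction: λ = 15 × 0.3267 / 0.5 = 9.8, power 79.6%.
- Joint: λ = 15 × 2 × 0.49 / (0.75 + 0.25) = 14.7, power 92.7%.

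Note that 4.9 + 9.8 = 14.7. The adjusted test gathers the information that the three-level model splits between its two terms.

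| Differences at 4, 8, 12 months (SD) | Main effect, % | Interaction, % | Joint adjusted, % |
|---|---|---|---|
| 0, 0.70, 0.70 (sustained) | 68 / 59 / 51 / 48 | 64 / 80 / 96 / 99.5 | 89 / 93 / 98 / 99.8 |
| 0, 0.70, 0.35 (fading) or 0, 0.35, 0.70 (delayed) | 45 / 37 / 32 / 30 | 51 / 67 / 88 / 97 | 73 / 80 / 92 / 98 |
| 0, 0.70, 0 (8 months only) | 23 / 19 / 17 / 16 | 64 / 80 / 96 / 99.5 | 72 / 83 / 96 / 99.5 |

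Entries run over ρ = 0.3 / 0.5 / 0.7 / 0.8.

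The baseline-adjusted 8-month difference alone has λ = 15·d8²/(1−ρ²), F(1,57). Its power is 80 / 87 / 96 / 99% when d8 = 0.70, but 29 / 34 / 46 / 60% in the delayed profile.

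**3. Per group for 90% power, sustained 0.70 SD:** main effect 53 / 66 / 79 / 85; interaction 55 / 40 / 25 / 17; joint 31 / 28 / 21 / 16.

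**4. Losses at ρ = 0.5, sustained 0.70 SD:** with 27 or 24 per group (10% or 20% lost), joint 90% or 85%, interaction 75% or 69%.

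**5. Narrowed baseline.** The entry rule on limb symmetry may reduce the 4-month spread. Take an assumed 4-month SD of 0.6 and a sustained 0.70 SD, and compare the interaction, F(2,57), with the joint test, F(2,56). With correlations of 0.3 with baseline and 0.6 between follow-ups, power is 76 against 81%. With 0.5 and 0.7, it is 87 against 87%.

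**6. Simulation check, 15,000 runs, ρ = 0.5** (main effect, interaction, joint, 8-month adjusted). With no effect, rejection rates are 0.050, 0.049, 0.048 and 0.051. With a sustained effect they are 0.586, 0.792, 0.920 and 0.861.

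**The case against.** The planned model is valid, and the protocol nowhere says that the main effect is the test. The same model yields the interaction, which is sound, and the choice of term is often left to an analysis plan that is not shown here. The 90% matches the main effect closely only with ρ = 0.5, a value not in the protocol. The 'as in SPSS' interaction needs no ρ, passes 90% at N = 56 (90.5%) and gives 92.5% at N = 60. The gain over the interaction is slight at high correlation (96 against 98% at ρ = 0.7) and may vanish if eligibility narrows the baseline. The joint test has two degrees of freedom and gives no single estimate. The objective 2 / objective 3 labelling is a separate matter.

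Most of this stands. The main-effect loss is one possible reading, and the stated power is not shown to be wrong. What remains is a criticism of something the protocol does fix: it lists the 4-month value as an outcome and names only anthropometric covariates, although baseline strength is available for everyone. The joint adjusted test had no less power than the interaction in any case tried. The labelling adds no weight to the baseline point, but it does mean that the power for strength needs restating.

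**Conclusion.** The point holds as one of efficiency and clarity, not bias. It should be fixed; confidence is medium.

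- **If a three-visit main effect is the test,** power for a sustained 0.70 SD post-treatment difference is 48 to 68% over ρ = 0.3 to 0.8, well below 90%, and it falls as ρ rises.
- **If the interaction is the test,** the loss is confined mainly to low and moderate correlation. At ρ = 0.5 it needs 40 per group, against 28 for the joint adjusted test and 30 planned.

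These figures rest on assumed equal correlations and variances, the assumed effect profiles and, except where stated, no losses. Because the protocol gives no correlation, the trial is not shown to be underpowered.

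**What to change.** Make 8- and 12-month quadriceps strength the outcomes, with 4-month strength as a covariate beside the anthropometric ones, in a model with group, visit and group-by-visit. Do not rest the conclusion on a group main effect that includes the 4-month visit.

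The sponsor should state whether the primary test is at 8 months, at 12 months or both jointly. Testing at 8 months alone is robust to an effect that fades after the tablets stop but loses power for a delayed one; 12 months alone does the reverse. The joint test is the compromise.

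Restate the power for strength (objective 3) on the chosen test, with its assumed correlation. With 30 per group and 90% power, the joint test needs a sustained 0.71 / 0.67 / 0.57 / 0.48 SD at ρ = 0.3 / 0.5 / 0.7 / 0.8. If the three-level model is kept, name the group-by-time interaction as the test; it needs 0.95 / 0.81 / 0.62 / 0.51 SD.

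The cost is wording and a restated power figure. No extra patients, visits or measurements are needed.

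### A Kolmogorov-Smirnov check of the trial data, not the plan, decides which test and which group contrast answer the primary question

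*Protocol*

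**What the plan says.** All of the analysis text is in the protocol's Data Processing and Analysis section. It gives one comparison of the two arms: "For objective 2, data will be analyzed by a repeated-measure ANCOVA (Control vs vitD supplementation; with repeated measures at 4-, 8-, 12-month post-op", with anthropometric variables as covariates. It then says: "Primary outcome would be quadriceps muscle strength". The next sentence sets the condition: "These statistical tests will be performed after checking the normal distribution with Kolmogorov-Smirnov test, otherwise, a non-parametric" equivalent is to be used. The fallback is not named. Nor does the text say whether the check applies to raw values or residuals, by arm or by visit, or at what threshold.

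The ANCOVA is labelled for objective 2, which concerns vitamin D status. Strength is objective 3 in the Objectives section ("To examine the effect of vitamin D supplements on the quadriceps muscle strength for patients after ACLR"), and no test carries that label. Reading the ANCOVA as the primary analysis is therefore an inference, but no other between-group analysis is given.

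The Sample Size Estimation section supports only the parametric model: with 30 per group, "a repeated-measure ANOVA (with three repeated measures) will have 90% power to detect at the 0.050 level, with an effect size of 0.35".

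**The concern.** The gate is a rule that the protocol itself states. A statistical analysis plan that follows the protocol would inherit it, so this is more than a detail left for later.

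Under the rule, the trial's own data select the test of the primary outcome. The contrast may change with the test. A repeated-measure ANCOVA has no single rank-based counterpart, and the candidates differ in whether they keep the covariates, the 4-month value and the repeated visits. The check also has the wrong target if it is applied to the data as they stand, because ANCOVA assumes approximate normality of residuals.

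At stake are a primary result that is not fully defined in advance and a power statement that does not cover one of the two branches.

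**Working it through.** **1. The stated power.** Inputs from the protocol: N = 60, m = 3 measures, f = 0.35, alpha 0.05. The correlation rho between visits is not given, so 0.5 is assumed and 0.3 and 0.7 are shown. For the between-group effect, lambda = N·m·f²/(1 + (m−1)·rho), with F on 1 and 58 df. At rho 0.5, lambda = 60·3·0.1225/2 = 11.025 and power is 0.904. At rho 0.3 and 0.7 it is 0.955 and 0.846. The 90% therefore reproduces as the group effect averaged over three visits. For two groups, f = 0.35 is a difference of 2·0.35 = 0.7 SD, here present at all three visits.

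**2. How often the gate would fail.** Simulated, 30 per arm, check at 0.05:

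| Check applied to | Normal data | Mild skew (lognormal, sigma 0.3) |
|---|---|---|
| six arm-by-visit cells, Lilliefors-corrected | 26% | 76% |
| three visits, arms pooled, corrected | 14% | 67–79% |
| model residuals, one check | 5% | 22% |
| six cells, uncorrected | about 0.1% or less | 2.5–2.8% |

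A separate simulation gave 25–27% for the six cells and 10–11% for the pooled visits with normal data.

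**3. Type I error.** With one fallback followed mechanically it was 0.047–0.053 over rho 0.3–0.7, for normal and skewed data.

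**4. The fallback matters.** Simulated power with normal data at rho 0.5 / 0.7 / 0.8, with the effect set for about 90% power of an ANCOVA adjusted for the 4-month value:
- that ANCOVA: 0.87 / 0.88 / 0.89
- rank ANCOVA: 0.84 / 0.84 / 0.82
- Mann-Whitney on change: 0.69 / 0.80 / 0.82
- Mann-Whitney on follow-up values: 0.70 / 0.52 / 0.37

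**5. The tested effect matters too.** Patients enter on a strength deficit relative to "of contralateral leg at 4-month isokinetic assessment", and supplementation starts after that, so the 4-month visit is untreated. Assume 0.7 SD at 8 and 12 months, zero at 4 months, equal correlation, normal data, n = 30 per arm, no drop-out, and anthropometric covariates ignored. At rho 0.5:
- Group effect over three visits: mean difference 0.7·2/3 = 0.467; variance of a patient's mean (1 + 2·0.5)/3 = 0.667; lambda = 15·0.467²/0.667 = 4.9; F(1,58) power 0.586 (simulation about 0.58).
- Group-by-time: the centred differences −0.467, 0.233, 0.233 have sum of squares 0.327; lambda = 15·0.327/(1 − 0.5) = 9.8; F(2,116) power 0.796 (simulation about 0.79).
- Mean of 8 and 12 months adjusted for 4 months: residual variance (1 + 0.5)/2 − 0.5² = 0.5; lambda = 15·0.49/0.5 = 14.7; F(1,57) power 0.965 (simulation 0.962).
- Mann-Whitney on the mean of 8 and 12 months: about 0.84 (simulation).

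The same formulas at rho 0.3 give 0.68, 0.64 and 0.945 for the first three, with Mann-Whitney about 0.9. At rho 0.7 they give 0.51, 0.96 and 0.99, with Mann-Whitney about 0.8.

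**The case against.** The strongest objection concerns power. A reader might infer that the gate costs power against the protocol's own analysis. The documents do not support that as a general claim. If the gate is applied to six corrected cells with a Mann-Whitney fallback, power at rho 0.5 falls from 0.96 to 0.93 (normal), from 0.96 to 0.91 (skewed, constant shift) and from 0.95 to 0.87 (skewed, proportional shift). The starting values, however, belong to an ANCOVA adjusted for the 4-month value, which the protocol does not specify. Against the stated model at rho 0.5, the Mann-Whitney's 0.84 exceeds both 0.586 and 0.796. It falls short of the group-by-time test at rho 0.7. A rank-transformed ANCOVA is arguably the nearer equivalent, and with it the switch gives 0.957, 0.967 and 0.947 against 0.962, 0.959 and 0.951, so one setting is a small gain. This objection stands, and no general power loss is claimed here.

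Three other stronger readings also fail:
- **Inflated type I error.** This would need a free choice between the two results, which gives 0.068–0.089. The protocol states a rule and does not offer that choice.
- **Frequent disagreement.** ANCOVA and Mann-Whitney disagree on significance in 9–12% of all trials at rho 0.5. The switch itself, under the gate that fails most often, changes the verdict in about 3% of trials with normal data and 7–10% with skewed data.
- **Loss of the adjusted estimate through the summaries.** Non-normal data are "except for non-normally distributed data which are reported as the median, minimum and maximum", which contains no adjusted group difference. The mean and standard error used for normal data contain none either. Both are descriptive formats.

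It can also be said that the fallback's name and the details of the check belong in a statistical analysis plan. That is fair, and their absence is not the point. The data-dependent switch is written into the protocol and remains whatever names are filled in later.

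**Conclusion.** The concern holds as a fault in how the primary analysis is fixed. The outcome of a normality check selects the test and possibly the contrast, and the protocol's power statement covers only one branch. Type I error is not at issue under a mechanical rule. The direction and size of any power effect depend on how the check is applied, the fallback, the correlation and which effect of the stated model is tested, and the protocol settles none of these.

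What can be quantified is the gain from fixing a baseline-adjusted contrast: about 0.96, against about 0.58 or 0.79 for the two readings of the stated model. It rests on an assumed rho of 0.5, normal data, no drop-out and a 0.7 SD effect absent at 4 months. The size of the gain varies with rho, and against the group-by-time test at rho 0.7 it is small (0.99 against 0.96). That the ANCOVA is the primary analysis remains an inference from the text, so confidence is medium.

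**What to change.** Delete the Kolmogorov-Smirnov gate for the primary outcome and state, for example:

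> The primary analysis of quadriceps strength is the vitamin D versus placebo difference over the 8- and 12-month visits, from a repeated-measures model adjusted for the 4-month (pre-treatment) value and the anthropometric covariates, with its 95% confidence interval, whatever any normality check shows. Residual plots are a diagnostic only. A rank-transformed ANCOVA with the same covariates is reported as a sensitivity analysis.

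Removing the gate alone takes one sentence. The rest of the wording goes further: the 4-month value moves from outcome to covariate, the contrast is fixed in advance, and one small sensitivity analysis is added. The power statement should then be restated for that contrast.

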## Method

### Intervention

For the proposed study, we will use 2000IU/day as advised by the Endocrine Society (4). Previous study has shown 2000 IU/day for 4 months showed significant improvement of muscle strength (5). Therefore, for the proposed study, we will use 2000 IU/day (a standard formulary used in Hospital Authority in our cluster), for a duration of 16 weeks.

Subjects will be randomized into 2 study groups:

Group 1: Placebo group

Group 2: Intervention group - patients receive daily dose of 2000 IU of vitamin D3 supplements

All study tablets including the placebo will be manufactured according to Good Manufacturing Practice (GMP) guidelines for quality assurance. They will be taken with water at breakfast, 2 tablets at a time and once daily. The treatment will last for 16 weeks after which the supplementation will be stopped. Subjects will continue with their usual lifestyles in diet and physical activity without receiving any other treatment for muscle health. The procurement of study tablets will be covered by departmental funding.

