#### 3. Radiological Assessment

##### (a) Magnetic Resonance Imaging (MRI)

Muscle volumes of quadricep muscle are measured using a 1.5 or 3.0 Tesla MRI Scanner. Axial (3mm thick cut) T1W images are obtained from the anterior superior iliac supine (ASIS) to patella. Quadriceps muscles were manually outlined in each axial slice. Muscle volume was calculated by summing all of the slice-multiplied by slice thickness. The quality of the muscle is assessed by analyzing the fat content of the muscle mass using technique that has been reported by Reeder et al (6). Bilateral legs will be performed before the start of the vitamin supplementation (4 months post-op) and with the injured side repeated after the completion of the 16-weeks supplementation (8 months postop).The uninjured side will be used as reference for 'normal volume'.

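### The analysis labelled Intention-to-Treat covers only patients who completed 16 weeks of treatment, and the protocol states no analysis of all randomised patients.

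*Protocol*

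**What the plan says.** Patient Recruitment & Eligibility sets the size and the randomisation: "60 participants will be recruited, with 30 in each group", and "Participants are randomly assigned into either the Vitamin D intervention group or the placebo-controlled group". Under Intervention, "The treatment will last for 16 weeks after which the supplementation will be stopped".

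Data Processing and Analysis names quadriceps strength as the primary outcome and plans a repeated-measures ANCOVA "with repeated measures at 4-, 8-, 12-month post-op". It then states that the Intention-to-Treat "principle will be followed for data analysis purposes on those who have completed 16-week treatment". One further analysis set follows, a protocol-evaluable analysis that "will also be conducted using the 80% compliance as the cut-off".

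The protocol describes no other analysis population.

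**The concern.** Intention-to-treat means that everyone randomised is analysed in the arm to which they were assigned. The sentence names that principle and then applies it only to treatment completers, so it contradicts its own label. Keeping completers in their assigned arms does not bring back the patients who were left out.

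The affected comparison is the primary one, in a trial with 30 patients per arm, where each excluded patient is 1/30, or about 3.3%, of an arm. If patients stop for reasons linked to their recovery, and do so differently on vitamin D and on placebo, the two completer groups are no longer comparable. The result would still be reported as intention-to-treat, and readers would credit it with a protection from randomisation that it does not have.

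**Working it through.** **1. The text.** Randomisation comes first and the 16-week course follows, so whether a patient completes is known only after randomisation. Two readings of completion are possible:

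- *Took tablets to the end.* Anyone who stops early is excluded.
- *Reached the end of the 16-week period, whatever the tablet intake.* Anyone who withdraws earlier is excluded.

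Either way the set is chosen by a post-randomisation event. The 80%-compliance set is too.

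**2. The plan's own power figure.** The sample size section says that with 30 per group "a repeated-measure ANOVA (with three repeated measures) will have 90% power to detect at the 0.050 level, with an effect size of 0.35". Two inputs are not stated and are assumed here: 0.35 is Cohen's f, and the correlation between repeated measures is ρ = 0.5. For the between-groups test with m = 3 measures,

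λ = f²·N·m / (1 + (m − 1)ρ), on 1 and N − 2 degrees of freedom.

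With N = 60: λ = 0.1225 × 60 × 3 / 2 = 11.025, and power is 0.904. The stated 90% is reproduced, but only if all 60 randomised patients contribute. The group-by-time version with the same inputs gives over 0.999, so it does not match the stated figure.

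**3. Illustration of the bias.** The protocol gives no non-completion rate, so every input here is assumed: no true effect, SD 1, 30 per arm, one endpoint, two-sided t-test, and non-completion p equal in both arms. Completers do better than non-completers by g SD in one arm and by 0 in the other. Each arm's overall mean is the same, so completers in the first arm sit p·g above it, and the expected shift is p·g. Simulation with 10,000 runs per case gave:

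| p (per arm) | g | p·g | Simulated shift, completers | False-positive rate, completers |
|---|---|---|---|---|
| 10% (3) | 0.5 | 0.05 | 0.053 | 5.3% |
| 10% (3) | 1.0 | 0.10 | 0.104 | 6.7% |
| 20% (6) | 0.5 | 0.10 | 0.100 | 6.4% |
| 20% (6) | 1.0 | 0.20 | 0.197 | 9.9% |
| 10% or 20% | 0 | 0 | 0.001 to 0.005 | 5.0% |

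Analysing all 60, each with a measured outcome, gave a shift between −0.001 and 0.004 and a rate of 4.3% to 4.9% in every case.

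A second mechanism gave similar values. Here poorer performers were selectively lost in one arm and loss was random in the other, with a correlation of 0.3 to 0.5 between outcome and dropping out. At 20% loss the bias was 0.10 to 0.17 SD and the rate 6.9% to 9.6%. At 10% loss it was 0.05 to 0.09 SD and 5.4% to 6.5%.

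**4. Power under each set.** Assume that patients who stop gain nothing, so that with all 60 analysed the effect becomes f(1 − p). With the formula in step 2 and ρ = 0.5:

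| Stopping | Completers only (N) | All 60, diluted effect |
|---|---|---|
| 0% | 0.904 (60) | 0.904 |
| 10% | 0.871 (54) | 0.836 |
| 20% | 0.828 (48) | 0.743 |
| 25% | 0.803 (45) | 0.688 |

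At 20% with all 60 analysed, f = 0.28 and λ = 0.0784 × 60 × 3 / 2 = 7.056, which gives 0.743. With ρ = 0.3 or 0.8 that figure is 0.832 or 0.630.

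**The case against.** Nobody reading the sentence can reconcile it with its label. The serious objections concern how much is at stake and how much the change would achieve.

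- **The near-zero bias with all 60 analysed assumes that non-completers are still measured.** This is right. Patients who stop tablets may also stop attending. At 20% non-completion and g = 1.0, if 3 of the 6 non-completers are unmeasured in each arm, the first arm's mean is (24 × 0.2 − 3 × 0.8)/27 ≈ 0.09 SD too high. If all 6 are unmeasured, the shift returns to about 0.20 SD and the rate to about 10%. A mixed model helps only so far as the missingness is explained by observed data. The benefit is therefore less bias, to the extent that non-completers are followed.
- **The consequence depends on what completion means.** If it means reaching week 16, many of those excluded may have no 8-month value anyway, and the practical difference is smaller. That stands, but the label is still wrong.
- **The trial is double-blind and placebo-controlled.** Blinding makes differential dropout less likely without ruling it out. With the same 1.0 SD gap in both arms at 20% non-completion, the shift is about 0 and the rate 4.9%.
- **The cost in power is real.** Under the dilution assumption at 20% stopping, about 92 patients rather than 60 would be needed to restore 90%. This rests on the between-groups test, which the protocol does not name; the group-by-time version still gives 0.998.
- **The SAP may settle this.** Missing-data handling and the choice of model are commonly left to a SAP. The analysis population is not open in that way, because the protocol fixes it. A SAP that analysed all randomised patients would contradict this sentence.

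**Conclusion.** The concern holds and should be corrected before the analysis. The set called intention-to-treat is a completers set under either reading of completion, and this protocol states no analysis of all randomised patients. That conclusion rests on the text alone and needs no assumption.

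The size of any bias cannot be known from the document. In the one-arm-gap illustrations at 10% to 20% non-completion it is about 0.05 to 0.20 SD, with false-positive rates of about 5% to 10%. These are examples, not bounds, and the bias is about zero if completion is unrelated to outcome or acts alike in both arms. The case for change is protection from selection bias and an honest label, not a gain in power.

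**What to change.** 1. Define the primary analysis set as all randomised patients in their assigned group, whether or not they completed the 16 weeks.
2. State that strength is measured at 8 and 12 months after surgery in everyone, including patients who stopped tablets, and that these visits do not depend on finishing the course. This needs saying because the MRI section has the scan "repeated after the completion of the 16-weeks supplementation (8 months postop", the anthropometric section also ties one assessment to the end of supplementation, and the isokinetic section gives no visit schedule.
3. Analyse with a method that keeps patients with partial data, for example a linear mixed model, which SPSS provides. The detail can sit in the SAP.
4. Rename the present set a completers analysis and keep it, with the 80%-compliance set, as supportive.

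**Cost.** This is mainly a wording change. It adds no patients and no visits beyond the 8- and 12-month time points already in the analysis model, but it does require effort to bring non-completers back for them. If those who stop gain nothing, the estimated effect is up to 10%, 20% or 25% smaller at those stopping rates. On the assumptions in the working, power at 20% stopping is 0.743, against 0.828 in completers. The sponsor should accept that loss knowingly or revisit the sample size.
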